9.4 Safety Population (SP)

The SP will include all subjects who have undergone insertion of an ablation catheter. The subjects will be analyzed according to the actual treatment received by subjects regardless of the Group they are randomized to. The calibration roll-in and discontinued roll-in cases will be included in the SP.

9.5 SNA Population (SNAP)

The SNAP will include all subjects who are enrolled and randomized within the Main Study and who further satisfy specific inclusion and exclusion criteria and provide additional consent to participate in the SNA. Eligible SNA subjects will have undergone RF delivery with the study ablation catheters and will have successfully completed pre- and post-ablation brain MRI examinations, NIHSS Questionnaires, and general neurological assessments.

9.6 SNA Evaluable Population (SNAEP)

SNA Evaluable Population includes subjects who have provided consent to participate in the SNA, satisfy specific eligibility criteria, receive RF ablation, had both the pre- and post- MRI performed and completed one or more post-ablation neurological assessments.

10.0 Sample Size Justification

Per protocol, trial simulation was carried out to evaluate the performance characteristics of the trial. For each scenario, 10,000 simulated trials were summarized to create the performance characteristics of that trial. Under the assumptions of equivalent effectiveness success rate at 55% and equivalent safety event rate at 8.6% in both groups, at an experiment-wise error rate of 0.05, an adaptive sample size of 250-500 (mean sample size of 417) will provide 80% power for trial success, meeting both effectiveness and safety endpoints, and 82.8% power and 87.4% power for meeting effectiveness and safety endpoints individually. The probability of early trial success is 36.8%. In the simulation, the non-inferiority margin is 15% for effectiveness and 8% for safety. The primary AE rate in the first 7-days is simulated as a Bernoulli random variable with a specified probability; the occurrence of effectiveness failure and timing of the failure are based upon a three-piece exponential time-to-failure model.

These trial simulations assume a primary AE rate of 8.6% for both Test and Control groups under the alternative hypothesis. Based on P030031/S011 data, the overall primary AE rate was 10.8%. However, this primary AE rate included 3 study subjects deemed primary safety failures solely due to hospitalization for AF recurrence. The incidence of primary AEs excluding those 3 subjects was 8.6%. Thus, an 8.6% primary AE rate is used for the purpose of trial simulations.

These trial simulations assume an equivalent success rate of 55% for both Test and Control groups under the alternative hypothesis using the chronic definition of effectiveness failures as defined in the protocol. These assumptions are based upon review of data from recent pivotal P030031/S011 AF THERMOCOOL® Trial where the chronic success rate in the NAVISTAR® THERMOCOOL® Group at 1 year follow-up was 62.7% (64/102) for all sites and 43.3% (29/67) for US data only. Therefore, it is estimated that the chronic success rate for both the nMARQTM System and THERMOCOOL® at 12-month follow-up will be around 55%.

The sample size in the Main Study may vary from 250 to 500 due to the adaptations to the trial.

As for the SNA sub-study, At least 60 subjects (≥30 Test subjects and ≥30 Control subjects) from the already enrolled and randomized subjects of the Main Study will be selected in sequence for the SNA. The sample size is not intended for statistical comparisons by treatment group; however, 30 subjects in each arm will provide at least 91% probability of observing at least one event if the true event rate is at 8-14%.

Therefore, the total sample size for this IDE study to be up to 777 subjects (500/0.95+250), based upon the 250-500 subjects required for the effectiveness evaluation, up to 250 Calibration Roll-in subjects and 5% potential subject attrition rate before randomization. Up to 250 roll-in subjects using the nMARQTM System are expected in this study because up to 50 sites will enroll up to 5 roll-in subjects each to reduce the influence of learning curve on effectiveness results. It is also estimated that no more than 5% of enrolled patients will either not meet the inclusion/exclusion criteria or be lost to contact or withdrawn prior to the randomization. The enrollment will be concluded when study outcomes meet the early stopping criteria or when 500 subjects have been randomized in the Main Study.

Per Closeout Plan, study enrollment will be stopped after receiving the FDA approval of the Closeout plan (dated Jul 18, 2017). The total sample size of the final CSR will be based on the actual enrollment status up to Jul 18, 2017. As for the SNA study, the enrollment has been halted after achieving total of 76 enrolled SNA subjects. The SNA final report was submitted and reviewed by FDA on Jan 21, 2016.

11.0 Data Monitoring Committee (DMC)

No Data Monitoring Committee will be constituted for the study.

12.0 Analyses to be Conducted

Per the Closeout Plan, a final Clinical Study Report (CSR) will be submitted to the FDA. The CSR will be formatted similar to an annual progress report. Descriptive statistics and data listing will be presented for demographic and baseline characteristics, subject disposition, ablation procedure data, device accountability and safety data. No inferential statistics will be performed. Efficacy data will not be reported. All the analysis methods described in the following sections are based on the Closeout Plan and will be performed for the CSR.

The SNA final analysis report, dated November 10, 2015, was submitted to the FDA on December 21, 2015 (G120289 / S012). The FDA approved the supplement on January 21, 2016 and determined that the enrollment cap could be removed based on the current results of the subpopulation neurological assessment. Therefore, the study results of the SNA sub-study won't be included in the final CSR.

12.1 General Conventions

Summary Statistics

For continuous variables (e.g., age), summary statistics will include the sample size (n), mean, standard deviation, and median, minimum, maximum, and quartiles.

For categorical and ordinal variables, summary statistics will include the sample size (n) and percentage (%) for each unique category. Confidence limits for binary variables, will be computed using the exact binomial distribution unless otherwise specified.

Study Days

The analysis of data will require that the number of days since the initial ablation is calculated. The Study Day will be calculated as: (date of the occurrence of event – initial ablation date).

Note: The day of initial ablation is considered Study Day 0. The "event" in the above definition includes: completion of/exit from the study, onset of AEs, etc.

Data Display

Data displays will include three types - summary tables, data listings and figures. Unless stated otherwise, data listings will be produced for all critical data points.

• Reporting of Numerical Values

Means, standard deviations, medians, and confidence intervals will be reported to one decimal place more than the data reported on the CRF or by the laboratory/vendor. Minimum and maximum will be reported to the same number of decimal places displayed on the CRF or by the laboratory/vendor.

• Statistical Software

SAS 9.3 and SAS studio will be used to execute the statistical analyses per this plan.

12.2 Subject Disposition

- Excluded Subjects: subjects who have signed the ICF, but are found to not meet the study eligibilities, PRIOR to insertion of the study catheter. Excluded subjects will not be included in either the effectiveness or safety analyses of the study catheters.
- **Evaluable Subjects**: all enrolled subjects who have the study catheter inserted. (Calibration Roll-in, discontinued Roll-in and randomized subjects.)
 - Discontinued Subjects: evaluable subjects who have the study catheter inserted but do not undergo ablation (i.e., no RF energy is delivered with the study catheter). Subjects will be categorized as "discontinued" if ablation is not possible due to equipment failure or if their arrhythmia is determined at the time of electrophysiology study to be a non-study arrhythmia; e.g., AFL instead of PAF (required for subject enrollment per study inclusion criteria). Discontinued subjects will remain in follow-up for 30 days as part of the safety

- cohort. If an SAE is reported for a discontinued subject, they will be followed until event resolution.
- Calibration Roll-in Subjects: enrolled subjects who have the study catheter inserted and RF delivered during the Calibration Roll-in Phase. These subjects will be included as part of the analyses for secondary safety endpoints but not analyses for the primary endpoints. Calibration roll-in cases are not randomized and will be limited to not more than 5 subjects enrolled and treated at each site.
- **Lost to Follow-up Subjects:** subjects who are enrolled and evaluable, but contact is lost after most recent follow-up visit (despite 3 documented attempts to contact the subject).
- Withdrawn / Early Termination Subjects: subjects who withdraw consent for study participation or are withdrawn by the investigator (as described in Section 6.10) or are terminated from the study prior to completion of all follow-up visits.
- Completed Subjects: enrolled subjects who have not been excluded, discontinued, expired, withdrawn, early terminated or lost-to-follow-up from the study prior to the final study visit.

Figure 1 summarizes the study enrollment and accountability and explains the subject flow.

[figure not shown]

Figure 1: Subject Flowchart

Disposition of all enrolled subjects will be summarized. Listing per subjects' reasons of exclusion, discontinuation, withdrawal/early termination due to study close out, and lost to follow-up will be provided.

12.3 Demographics and Baseline Characteristics

Demographics data, including age, gender, race and ethnicity, will be summarized overall and by treatment group for the enrolled subjects, randomized subjects and roll-in subjects.

Baseline characteristics, including Medical History, Atrial Fibrillation History, CHADS2 score, Canadian Cardiovascular Society Severity in Atrial Fibrillation (CCS-SAF) scale, Failed AAD Medication History at screening, TTE Exam, Visualization of LA Thrombus assessment, and ECG, will be summarized overall and treatment group for all enrolled subjects, randomized subjects and roll-in subjects. Descriptive statistics for continuous and categorical variables will be presented.

12.4 Endpoint Analyses

Descriptive statistics and two-sided 95% confidence intervals will be presented for the safety data. Analyses of safety data will be performed in the proposed analysis populations excluding the subjects with missing outcomes.

12.4.1 Primary Safety Endpoints

The incidence of early-onset Primary Adverse Events is the percentage of patients with at least one primary adverse event with onset on Day 0 through Day 7 except for pulmonary vein (PV) stenosis and atrio-esophageal fistula that could occur greater than one week (7 days) post-procedure. The number of primary adverse events (PAE) and the number of subjects experiencing primary adverse events will be reported.

The primary safety outcomes will be presented in the SP, AT populations and for Calibration Roll-in subjects. Listing of PAEs will be provided for subjects in SP.

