8.0 Study Endpoints

8.1 Primary Safety Endpoint

The primary safety endpoint for this study is the incidence of early-onset (within 7 days of the ablation procedure) primary AEs.

Death	Pericarditis requiring intervention (major)
Myocardial infarction (MI)	Cardiac Tamponade/Perforation
Pulmonary vein (PV) stenosis [†]	Pneumothorax
Diaphragmatic paralysis	Vascular Access Complications
Atrio-esophageal fistula [†]	Pulmonary edema
Transient Ischemic Attack (TIA)	Hospitalization (initial and prolonged)*
Stroke/Cerebrovascular accident (CVA)	Heart block
Thromboembolism	

*Excludes hospitalization (initial & prolonged) solely due to arrhythmia (AF/AFL/AT) recurrence or due to non-urgent cardioversion (pharmacological or electrical). Refer to Table 10.1.3A for definitions of the Primary AEs.

[†]Pulmonary vein (PV) stenosis or atrio-esophageal fistula that occurs greater than one week (7 days) post-procedure shall be deemed a Primary AE.

Refer to Table 10.1.6A for a comprehensive list of anticipated adverse events.

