10.1.3 Primary Adverse Event

A **Primary AEs** is an event listed in Table 10.1.3A which occurs within the first week (7 days) following an ablation procedure. Primary AEs are considered SAEs.

Table 10.1.3A: Primary Adverse Events

Primary Adverse Event	Description/Criteria
Death	Adverse event resulting in patient death.
Atrio-esophageal Fistula*	Connection between the atrium and the lumen of the esophagus as evidenced by documentation of esophageal erosion combined with evidence of a fistulous connection to the atrium.
Cardiac Tamponade/Perforation	The development of a significant pericardial effusion during or within 30 days of undergoing the index AF ablation procedure. A significant pericardial effusion is one which results in hemodynamic compromise [†] , requires elective or urgent pericardiocentesis, or results in a 1 cm or more pericardial effusion as documented by echocardiography. 
 Cardiac tamponade/perforation should also be classified as: 
 Early – diagnosed prior to discharge Late – following initial discharge from the hospital (see Safety requirement below)
Myocardial Infarction	Presence of any one of the following criteria: 
 Detection of ECG changes indicative of new ischemia (new ST-T changes or new LBBB) which persist for more than 1 hour Development of new pathological Q waves on ECG Imaging evidence of new loss of viable myocardium or new regional wall motion abnormality
Stroke	Stroke/CVA is an acute symptomatic episode of neurological dysfunction attributed to a vascular cause (ischemia or hemorrhage) in which symptoms last more than 24 hours, or if symptoms last less than 24 hours, a brain imaging study demonstrates infarction.
Cerebrovascular Accident (CVA)	
Thromboembolism	Formation in a blood vessel of a clot (thrombus) that results from the breaking loose of all or part of an existing thrombus, which is then carried by the blood to lodge in/occlude a more distal vascular site.
Transient Ischemic Attack	Acute episode of temporary (<24 hrs) and focal loss of cerebral function of vascular (occlusive) origin as determined by the consulting neurologist.
Diaphragmatic Paralysis	Change in baseline diaphragmatic functioning as evidenced by elevation of the diaphragm above the normal range but not due to a pulmonary process such as atelectasis.

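### SAP 12.4.1 counts most primary adverse events only in the week after the initial ablation, while protocol 10.1.3 counts from any ablation procedure; the anchor should be stated and both rates shown

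*SAP*

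**What the plan says.** - **Counting rule.** SAP 12.4.1 defines the incidence as the "percentage of patients with at least one primary adverse event with onset on Day 0 through Day 7". The same sentence exempts PV stenosis and atrio-esophageal fistula; those two may count later.
- **Day 0.** SAP 12.1 states that "The day of initial ablation is considered Study Day 0". Its list of events dated this way is "completion of/exit from the study, onset of AEs, etc", so adverse event onset is included.
- **Event definition.** Protocol 10.1.3 defines a Primary AE as an event in its table "which occurs within the first week (7 days) following an ablation procedure".
- **Endpoint statement.** Protocol 8.1 gives the endpoint as the "incidence of early-onset (within 7 days of the ablation procedure) primary AEs", and SAP 7.1 uses the same wording. Neither says index or any.
- **Repeats.** Protocol 9.12 leaves repeat ablation to the investigator's judgement. Under protocol 8.2, up to two repeats in the blanking period (Day 0-90) do not by themselves make a subject an effectiveness failure if the assigned system is used. SAP 6.0 keeps the visit schedule on the index procedure after a repeat.
- **Tamponade.** Protocol Table 10.1.3A describes it as arising "during or within 30 days of undergoing the index AF ablation procedure".

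**The concern.** The SAP fixes an anchor that the protocol's event definition does not. Repeat ablation is an expected part of this trial, and it carries procedural risk of its own. Under the SAP rule, a listed event in the week after a repeat is left out of the primary safety percentage. Under protocol 10.1.3 it is still a Primary AE, so it does not belong in the Serious Non-Primary category of SAP 12.4.2 either.

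This matters more than usual because SAP 12.0 drops efficacy reporting. The safety rate, shown with a two-sided 95% confidence interval, is the only primary endpoint left in the report. If it omits harm from repeats, it understates cumulative procedural risk. If repeat rates differ between arms, it also distorts the description of the arms. The SAP is dated December 2017, after the July 2017 closeout approval that opened the data to the blinded team (SAP 5.3), so the counting rule should be explicit and traceable to the protocol.

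**Working it through.** The documents give no figure for events after repeats, so there is none to reproduce. The check has two parts: a reading of the texts, and an illustration of size.

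**1. One case under each text.** Take a stroke, or a vascular access complication that meets the table's criteria, three days after a repeat ablation on Day 60.

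| Text | Anchor | Result |
|---|---|---|
| Protocol 10.1.3 | any ablation procedure | 3 days after the procedure, so a Primary AE |
| Protocol 8.1, SAP 7.1 | not specified | cannot be decided |
| SAP 12.1 with 12.4.1 | initial ablation | Study Day 60 + 3 = 63, outside Day 0-7, not in the percentage |
| SAP 12.4.2, Serious Non-Primary | event must be non-primary | does not fit |
| SAP 12.4.2, all AEs | any AE | included |
| SAP 12.4.1, count and listing of primary AEs | no day limit restated | may be included |

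The count of primary AEs and the percentage in SAP 12.4.1 could therefore disagree, depending on which definition the programmer applies to each.

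**2. Illustrative size.** Inputs:
- p = 8.6%, the planned primary AE rate (protocol 11.3.1). It is assumed here to apply to each procedure, index or repeat, independently.
- r = share of subjects with one repeat. The trial's own value is not in the documents. The range of 5% to 27% is an assumption; its top is the share with more than one procedure in the 2005 global survey cited in protocol 3.1.2.

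Subjects who already had an index event are not counted twice, so:

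rate counting repeats = p + r × p × (1 − p), with p × (1 − p) = 0.086 × 0.914 = 0.0786

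| r | Added (points) | Rate counting repeats | Share of affected subjects left out by index-only rule |
|---|---|---|---|
| 5% | 0.39 | 8.99% | 4.4% |
| 10% | 0.79 | 9.39% | 8.4% |
| 20% | 1.57 | 10.17% | 15.5% |
| 27% | 2.12 | 10.72% | 19.8% |

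**3. Difference between arms.** It shifts by 0.0786 × (gap in repeat rates). A gap of 5 points gives 0.39 points; a gap of 17 points (10% against 27%) gives 1.34 points. Nothing in the documents indicates that such a gap exists.

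**The case against.** The best defence is that an index-only window is a reasonable reading. The 7-day telephone call for primary AEs in protocol 9.8 belongs to a schedule that does not restart after a repeat. The simulations in protocol 11.3.1 draw a single 7-day safety outcome. SAP 2.0 says its methods replace the protocol's. This stands to the extent that neither anchor can be called the wrong one. It does not remove the mismatch: none of these texts says that events after repeats are excluded on purpose, SAP 7.1 restates the endpoint without the word index, and the protocol does write index where it means it, as in the tamponade entry.

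A reader might also infer more than the documents support:

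- **That a tamponade after a Day 60 repeat is dropped.** Table 10.1.3A ties tamponade to the index procedure, so that case does not meet the protocol's own description.
- **That all event types are affected.** PV stenosis and fistula are exempt from the window and still count after a repeat.
- **That the events vanish from the report.** They fall under all AEs, and the count and listing of primary AEs carry no stated day limit. Repeat procedures are also tabulated by arm and time (SAP 12.4.3).
- **That the omission uses up part of the 8% safety margin.** The margin applies to the difference between arms, where similar omissions largely cancel. SAP 8.0 also withdraws all formal hypotheses.
- **That late tamponade adds a known amount.** The documents give no share of tamponades arising on Days 8-30, so no figure can be put on it.

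**Conclusion.** The mismatch is real but limited. For every primary AE except PV stenosis and fistula, the SAP percentage rests on a window from the initial ablation. Protocol 10.1.3 uses any ablation procedure, and the endpoint statements do not decide between them. It cannot be concluded that the SAP contradicts a uniform protocol rule, because the protocol itself is not uniform.

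The likely effect on the reported rate is modest: about 0.4 to 2.1 percentage points on 8.6%, if 5% to 27% of subjects have one repeat at the same risk as the index procedure. The upper end leans on an old survey in a different population, and the closeout shortened follow-up to 3 months for some subjects (SAP 6.0). The change would affect a descriptive rate and its interval, not a trial decision. It is still worth making, because this is the only primary endpoint reported.

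The tamponade wording is a smaller, separate inconsistency. The table describes a 30-day window and a late class, while the governing sentence limits Primary AEs to 7 days and exempts only fistula and PV stenosis.

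**What to change.** In SAP 12.4.1:

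1. Report the subject-level primary AE rate with its 95% confidence interval in two rows: onset Day 0-7 after the index procedure, and onset Day 0-7 after the index or any repeat study ablation. Keep PV stenosis and fistula as already defined in both rows.
2. Label which row is the primary endpoint, and say what counts as a study ablation for repeats after the blanking period.
3. Say which definition governs the count and the listing of primary AEs, and where a primary AE after a repeat is placed in the SAP 12.4.2 tables.
4. Reconcile the wording with protocol 8.1 and 10.1.3, including the 30-day, index-based tamponade description against the 7-day limit.

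The cost is some SAP text and one extra derivation. SAP 12.4.3 already needs the dates of repeat procedures, so no new data are required. The second rate may look slightly less favourable; showing both avoids a dispute over the anchor.

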6.9 Subject Status and Disposition Definitions

All criteria listed below apply to both the Test and Control Groups.

Screen Failure: subjects that are screened, but do not meet eligibility criteria and have NOT signed an ICF. Screen failures should be captured in the electronic database. No data will be collected, only the date of screening and the reason for exclusion.

Enrolled Subjects: all subjects who sign the study ICF.

- **Excluded Subjects:** subjects who have signed the ICF, but are found to not meet the study eligibilities, PRIOR to insertion of the study catheter. Excluded subjects will not be included in either the effectiveness or safety analyses of the study catheters.
- **Evaluable Subjects:** all enrolled subjects who have the study catheter inserted. (Calibration Roll-in and randomized subjects.)
 - **Discontinued Subjects:** evaluable subjects who have the study catheter inserted but do not undergo ablation (i.e., no RF energy is delivered with the study catheter). Subjects

will be categorized as “discontinued” if ablation is not possible due to equipment failure or if their arrhythmia is determined at the time of electrophysiologic study to be a non-study arrhythmia; e.g., AFL instead of PAF (required for subject enrollment per study inclusion criteria). Discontinued subjects will remain in follow-up for 30 days as part of the safety cohort. If an SAE is reported for a discontinued subject, they will be followed until event resolution.

- **Calibration Roll-in Subjects:** enrolled subjects who have the study catheter inserted and RF delivered during the Calibration Roll-in Phase. These subjects will be included as part of the analyses for secondary safety endpoints but not analyses for the primary endpoints. Roll-in cases are not randomized and will be limited to not more than 5 subjects enrolled and treated at each site.
- **Lost to Follow-up Subjects:** subjects who are enrolled and evaluable, but contact is lost after most recent follow-up visit (despite 3 documented attempts to contact the subject).
- **Withdrawn / Early Termination Subjects:** subjects who withdraw consent for study participation or are withdrawn by the investigator (as described in Section 6.10) or are terminated from the study prior to completion of all follow-up visits.
- **Completed Subjects:** enrolled subjects who have not been excluded, discontinued, withdrawn, early terminated or lost-to-follow-up from the study prior to the final study visit.

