9.2 As-Treated Population (AT)

The AT subject population will include all randomized patients who have the ablation catheter inserted. They will be categorized by the treatment received if this deviates from the treatment randomized. Calibration Roll-in cases will not be included.

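### Roll-in adverse event tables are limited to roll-ins who received RF, while the AT and Safety Populations include subjects on catheter insertion alone

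*SAP*

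**What the plan says.** SAP 12.4.1 names three presentations of the primary safety outcome: "The primary safety outcomes will be presented in the SP, AT populations and for Calibration Roll-in subjects". SAP 12.4.2 names the same three groups for the 12-month and the second- and third-year adverse event tables.

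SAP 12.2 defines Calibration Roll-in subjects as "enrolled subjects who have the study catheter inserted and RF delivered during the Calibration Roll-in Phase". It defines discontinued subjects as those with insertion but no RF delivery. Its breakdown of evaluable subjects has three parts: "Calibration Roll-in, discontinued Roll-in and randomized subjects". SAP 9.4 keeps the same split: "The calibration roll-in and discontinued roll-in cases will be included in the SP".

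For randomized subjects the rule is insertion only (SAP 9.2): "The AT subject population will include all randomized patients who have the ablation catheter inserted". Protocol 6.1 also counts roll-ins by insertion, since only a subject excluded before the nMARQ catheter goes in fails to count. On follow-up, Protocol 6.9 says: "Discontinued subjects will remain in follow-up for 30 days as part of the safety cohort".

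**The concern.** Whether RF was delivered is known only after the catheter is in. Some harms need no RF. Protocol 4.1 describes perforation from catheter manipulation and vessel injury from catheter insertion, and both kinds of event are primary AEs in Protocol Table 10.1.3A. If such an event occurred in a roll-in who never received RF, it would be missing from the roll-in table. The same event in a randomized subject would be counted in AT.

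The roll-in table matters somewhat more because of what the close-out plan removed. The learning-curve subset analyses of Protocol 11.5.5 are not carried over, and SAP 12.8 allows no subgroup other than treatment group. The roll-in table is then the only separate estimate of learning-phase safety, and under SAP 12.4 it carries a 95% confidence interval.

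**Working it through.** **Inclusion rules side by side**

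| Set | Insertion required | RF required | Discontinued subjects in? |
|---|---|---|---|
| SP (SAP 9.4) | yes | no | yes, discontinued roll-ins named |
| AT (SAP 9.2) | yes | no | yes, randomized only |
| Calibration Roll-in (SAP 12.2) | yes | yes | no |

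It follows that SP = AT + calibration roll-ins + discontinued roll-ins. The last term has no column of its own.

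**Documents' own figures, reproduced**
- Roll-in ceiling (SAP 10.0): 50 sites × 5 = 250.
- Earlier nMARQ study (Protocol 3.3.3): primary AEs 9/163 = 5.5%, exact upper 95% limit 10.2%, as stated there. No RF delivered: 3/163 = 1.8%.
- Planning primary AE rate (SAP 10.0): 8.6%.

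**Direction of the shift**

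Let n roll-ins with RF have x events, and d roll-ins without RF have e events. Then

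x/n − (x + e)/(n + d) = [d/(n + d)] × (x/n − e/d).

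The displayed rate is too low only if e/d is larger than x/n. If e/d is smaller, the displayed rate is too high.

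**Illustration**

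Assumptions: 250 inserted roll-ins; 250 × 3/163 = 4.6, taken as 5 without RF; about 8.6% among the 245 with RF, taken as 21 events. The displayed rate is 21/245 = 8.6% (exact 95% CI 5.4 to 12.8).

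| Events among the 5 | All inserted | Exact 95% CI | Displayed minus all inserted |
|---|---|---|---|
| 0 | 21/250 = 8.4% | 5.3 to 12.6 | +0.2 points |
| 1 | 22/250 = 8.8% | 5.6 to 13.0 | −0.2 points |
| 2 | 23/250 = 9.2% | 5.9 to 13.5 | −0.6 points |
| 5 | 26/250 = 10.4% | 6.9 to 14.9 | −1.8 points |

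The break-even is 5 × 21/245 = 0.43 events.

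**Range over other assumptions**

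These use 150 roll-ins (the figure in the lower enrolment total of Protocol 6.4) or 250, and a rate among RF-treated subjects of 5.5% or 8.6%.
- With 1.8% not given RF, the difference is +0.1 to +0.2 points if none of them has an event, −0.2 to −0.6 with one event, and −1.8 to −1.9 if all have one.
- With 5% not given RF, it runs from +0.3 to +0.5 points (no events) to −4.4 to −5.0 points (all have events).

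**The case against.** A reader might infer that the table makes learning-phase safety look better than it was. The documents do not support that. Leaving these subjects out shrinks numerator and denominator together, and with no events among them the displayed rate is slightly worse. The discontinuation reasons named in SAP 12.2 are equipment failure and a non-study arrhythmia, not complications. Protocol 3.3.3 does not say why the three subjects without RF were not ablated, or that any of them had a primary AE. A higher event rate in this group is plausible but not shown.

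Nor are the events hidden. SAP 9.4 places discontinued roll-ins in the SP, and SAP 12.4.1 adds: "Listing of PAEs will be provided for subjects in SP". SAP 12.2 also calls for a listing of reasons for discontinuation. Apart from subjects dropped for missing outcomes, the group can be recovered by subtracting AT and calibration roll-ins from SP.

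Two further points carry weight. The table shells are not among the documents available here, and SAP 12.3 and 12.4.3 refer to roll-in subjects without the calibration label, so the programmed tables may already be wider than the text. The report is also descriptive only (SAP 8.0), roll-ins are outside the primary endpoint analyses, and no test of roll-in against AT is planned.

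These arguments dispose of a claim of favourable bias and limit the importance of the point. They do not remove the mismatch in the written definitions. A reader should not have to rebuild a safety denominator by subtraction.

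**Conclusion.** The mismatch stands on the literal text: the roll-in adverse event tables require RF delivery, and AT and SP do not. Its effect on the roll-in rate has no known direction. It is probably small: under the central illustration, +0.2 points with no event among five discontinued roll-ins and −0.6 points with two, well inside the confidence interval of the displayed rate. The extreme case of an event in all five gives −1.8 points. These sizes rest on assumed counts. The 250 is a ceiling in a trial that stopped early, the 1.8% comes from all nMARQ subjects in another study, and neither the number of discontinued roll-ins nor their events is given. No hypothesis or trial decision depends on the point. Severity: minor.

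**What to change.** In the adverse event tables of SAP 12.4.1 and 12.4.2, define the roll-in column as all roll-in subjects with the study catheter inserted, calibration plus discontinued. Alternatively, keep the present column and add a discontinued roll-in row with its n and events, so that the parts add up to SP. Because discontinued subjects are followed for only 30 days, footnote how many of them remain in the denominators of the later time windows. The 3-month PV-narrowing table can stay limited to subjects who received RF.

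The cost is one line in the SAP and a small change to the table shells. No new data are needed, since these subjects are already in the safety follow-up. The roll-in rate may move slightly in either direction.
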